## 2.8. Handling Rules for PD Data

For  $\alpha 4\beta 7$  and  $\alpha 4\beta 1$  receptor occupancies, and relative CCR9 mRNA expression which are collected at Visit 5 (Week 12),

- If participants are randomized into Group 2 (MORF-057 100 mg B.I.D. – MORF-057 100 mg B.I.D) or Group 3 (MORF-057 100 mg Q.D.-M – MORF-057 100 mg Q.D.-M), all data collected at Visit 5 (Week 12) will be considered as valid and included in the table summary for the Induction Period analysis.
- If participants are randomized to Group 1 (MORF-057 200 mg B.I.D. – MORF-057 100 mg B.I.D.) or Group 4 (Placebo – MORF-057 200 mg Q.D.-E), any data collected after the first maintenance dose will be considered as invalid and not be included in the table summary but provided in the listings.

### **3. ANALYSIS POPULATIONS AND APPLICATIONS**

#### **3.1. Full Analysis Set (FAS)**

The Full Analysis Set (FAS) includes all randomized participants who received at least one dose of study drug (MORF-057 or Placebo).

The FAS population will be used as the primary analysis population for all efficacy endpoints. Participants will be analyzed according to the treatment group they were randomized into.

#### **3.2. Per Protocol (PP) Population**

The Per Protocol (PP) Population is defined as all participants in the FAS Population who did not have any major protocol deviations related to the primary or secondary efficacy endpoint analyses.

All decisions to exclude participants for the PP Population will be made prior to the unblinding of the study. The PP Population may be used for sensitivity efficacy analyses of, at a minimum, the primary efficacy endpoint.

Participants in the PP population will be analyzed according to the randomized treatment group.

#### **3.3. Safety Population**

The Safety Population includes all participants who receive at least one dose of study drug (MORF-057 or Placebo).

The safety analysis population will be used for safety analysis. Participants will be analyzed according to the actual treatment received (see Section 6.2 for details). Randomized participants will be excluded from the safety analysis population only if there is documented evidence that participants have not taken any of study drugs (MORF-057 or placebo).

In addition,

- If a participant randomized to the placebo group receives MORF-057 by mistake during the 12-week Induction Period, his/her data for the Induction Period analysis will be included in the MORF-057 dose group in which he/she was treated for the longest duration.
- If a participant randomized to a MORF-057 dose group receives a different MORF-057 dose by mistake during the 12-week Induction Period, his/her data for the Induction Period analysis will be included in the MORF-057 dose group in which he/she was treated for the longest duration.
- If any participants receive a MORF-057 dose different from the one expected in the protocol by mistake during the Maintenance Period/Maintenance Extension Period, their actual maintenance dose group will be based on the MORF-057 dose in which they were treated with the longest duration.

#### **3.4. Pharmacokinetic (PK) Population**

The PK Population includes all randomized participants who received at least one dose of study drug and had at least one measurable PK concentration.

The PK Population will be used for PK data analysis.

### 3.5. Pharmacodynamic (PD) Population

The PD Population is defined as all randomized participants who received at least one dose of study drug and had at least one measurable post-dose PD measurement and its corresponding pre-dose PD measurement for, at minimum, one of the PD biomarkers.

The PD population will be used for the summarization of PD endpoints.

### 3.6. Application of Analysis Populations

Participants' demographics, baseline characteristics, UC disease history, study drug exposure and compliance, safety and efficacy endpoints will be summarized for the following populations.

**Table 4: Application of Analysis Populations**

Type	FAS	Safety Population	PP Population
Demographic and baseline characteristics	X		X
Medical history	X		
UC disease history	X		X
Protocol deviations	X		
Prior and concomitant medications	X		
Extent of treatment exposure and compliance		X	
Primary efficacy endpoint analysis	X		X
Secondary efficacy endpoints analysis	X		X
Exploratory efficacy endpoint analysis	X		
Subgroup analysis for 
 
• Primary efficacy endpoints
 
• Secondary efficacy endpoints
 
	X		
Safety Analysis (TEAEs, lab, vital sign, and ECG)		X	

FAS: Full Analysis Set; PP: Per-Protocol.

## 4. STATISTICAL ANALYSIS

All analyses described in this plan are considered as a prior analysis in that they have been defined prior to database lock. Any additional analysis performed after database lock will be considered as post hoc analysis and may be described as exploratory analyses in the clinical study report (CSR) as needed.

All summaries and statistical analyses will be performed using SAS v9.4 or later.

Continuous variables will be summarized with number of participants (n), mean, standard deviation (SD), median, first quantile (Q1), third quantile (Q3), minimum (min) and maximum (max). In addition, coefficient of variation (CV%) and geometric mean with CV% will be reported for summary of serum concentration and PD parameters.

Unless otherwise specified, mean, geometric mean, median, Q1 and Q3 will be reported to one more decimal than the raw data. The standard deviation (SD) will be reported to two more decimals than the raw data. CV% will be reported to 1 decimal and min and max will be reported as raw data. The confidence interval will be reported using the same number of decimals as the raw data.

Categorical variables will be tabulated by number of participants (n) with percentage (%) of the total number of participants for a given category of the analysis population. Participants with missing data are not included in calculations of percentages, except in the primary analyses of binary efficacy variables using the NRI method as specified in Section 4.8, or unless otherwise specified. Percentage will be reported to one decimal place. The confidence interval (CI) for the proportion will be calculated using the normal approximation approach when reported, unless otherwise specified.

Unless otherwise specified, the data for the Induction Period Analysis (see Section 1.5.1) will be presented by MORF-057 dose groups during the Induction Period and placebo, i.e.,

- 200 mg B.I.D.
- 100 mg B.I.D.
- 100 mg Q.D.-M
- Placebo

For the 52-week Treatment Period Analysis (see Section 1.5.2), the cumulative data, including the data from both the Induction and Maintenance Periods, will be used for participants initially randomized into an active MORF-057 treatment group and presented by treatment groups denoted by induction MORF-057 dose followed by maintenance MORF-057 dose, i.e.,

- 200 mg B.I.D. - 100 mg B.I.D.
- 100 mg B.I.D. – 100 mg B.I.D
- 100 mg Q.D.-M – 100 mg Q.D.-M.

For participants initially randomized into the placebo group during the Induction Period and subsequently switched to MORF-057 treatment (i.e., 200 mg Q.D.-E) during the Maintenance Period, unless otherwise specified, only the data collected during the Maintenance Period will be used in the 52-week Treatment Period Analysis to evaluate the effect of MORF-057 200 mg Q.D.-E. The data will be presented in the treatment group denoted by 200 mg Q.D.-E.

The data for the 104-week Total Treatment Period Analysis (see Section 1.5.3) will be presented by treatment groups similar to the 52-week Treatment Period Analysis described above, unless otherwise specified. All data during the 104-week Total Treatment Period will be used in the analysis for participants initially randomized to an active MORF-057 treatment group, and only the data during the Maintenance and Extension Periods will be used for participants initially randomized to placebo and subsequently switched to MORF-057 for maintenance treatment.

Unless otherwise specified, only scheduled visits including re-allocated visits (EOT or unscheduled visits, as described in Section 2.3) will be included in all by-visit analyses of efficacy and safety data. For the group of participants initially randomized to placebo and subsequently switched to MORF-057 for maintenance treatment, only the visits after Visit 5 (week 12) will be included in the by-visit analyses for the 52-week Treatment Period Analysis and the 104-week Total Treatment Period Analysis.

Data that are not summarized will be listed only. All data will be listed as collected for all randomized participants and will be ordered by randomized treatment group and visit if applicable.

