## 1.2. Study Design

This study is a randomized, double-blind, placebo controlled, multicenter, Phase 2b study to evaluate the efficacy and safety of 3 active dose regimens of MORF-057 (as capsule, P.O.) versus matching placebo in study participants with moderately to severely active UC.

Approximately 280 participants will be randomized into the treatment groups in a 1:1:1:1 ratio (i.e., 70 participants per group). The study will enroll participants who are advanced therapy naïve (i.e., have no previous exposure to an advanced therapy treatment for UC) and advanced therapy experienced (excluding vedolizumab), with at least 30% but no more than 40% of advanced therapy experienced participants. Randomization stratification factors will include baseline MES (<3 vs 3) and previous use of advanced therapy treatment (advanced therapy naïve vs advanced therapy experienced). All participants will be enrolled from approximately 150 centers worldwide. For this study, moderately to severely active UC will be defined as having an mMCS of 5 to 9 (inclusive), with an MES  $\geq 2$  (confirmed by central reader).

The main part of this Phase 2b study will consist of a Screening Period (up to 6 weeks, consisting of Stage 1 and Stage 2 testing), a Treatment Period (52 weeks, including a 12-week Induction Period and a 40-week Maintenance Period), and a Safety Follow up (SFU) Period (4 weeks).

During the main part of this study, there will be approximately 11 scheduled study visits: Screening Visit(s) (Visit 1 at Weeks 6 to 1), multiple Treatment Visits (Visits 2-10 at Weeks 0, 2, 6, 12, 18, 24, 32, 42, and 52 [End of Treatment (EOT)]), and an SFU Visit (visit to occur 4 weeks after the last dose of study drug is received, which will be at Week 56 if the full Treatment Period is completed or earlier if treatment is discontinued early). Study Day 1 represents the first day of the Treatment Period (i.e., when the participant will receive the first dose of study drug).

All participants who complete the 52-week Treatment Period will have the opportunity to continue their treatment in a 52-week Maintenance Extension Period.

During the optional Maintenance Extension, there will be 5 scheduled visits: 4 Treatment Visits (Visits 11-14 at Weeks 65, 78, 91, and 104 [EOT]) and an SFU Visit (visit to occur 4 weeks after the last dose of study drug is received, which will be at Week 108 if the full Maintenance Extension is completed or earlier if treatment is discontinued early).

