### 1.3. Sample Size and Power

The sample size was determined based on the primary endpoint of clinical remission at Week 12 by using the Chi-Squared Test to compare two proportions. A sample size of 70 participants per group (giving a total of 280) will provide 80% power to detect a difference of 15% in the clinical remission rate between MORF-057 and placebo, based on the use of a two-sided test at the alpha=0.10 level of significance. The calculation is based upon an assumed placebo remission rate of 7%.

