#### 4.8.4. Subgroup Analysis for Primary and Secondary Efficacy Endpoints

Subgroup analyses for the primary and secondary efficacy endpoints will be performed for the following baseline factors based on FAS:

- Age (< 65,  $\geq 65$ )
- Sex (male, female)
- Race (white, non-white)
- Prior use of advanced therapy treatment (naïve vs experienced)
- Baseline MES score (<3 or 3)
- Baseline mMCS score ( $\leq 7$  or  $> 7$ )
- Corticosteroid use at baseline (yes/no)
- Immunomodulator use at baseline (yes/no)

The point estimates of risk difference between MORF-057 and placebo groups with 95% CIs will be computed across the subgroups defined for each of the above factors. The computation will be based on the stratified risk difference using the Cochran-Mantel-Haenszel (CMH) weights, following a similar approach as used for the primary and secondary efficacy endpoints in the overall population. The stratification factors include baseline MES (<3 vs 3) and previous use of advanced therapy treatment (naïve vs experienced). In the case that the subgroup factor is identical or similar to a stratification factor (e.g., baseline MES score, and Prior use of advanced therapy treatment), only the stratification factor distinct from the subgroup factor will be used in the calculations.

Forest plots will be provided for subgroup analysis.

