## 6.5. The Calculation of Stratified Risk Difference Between Two Groups Using the Cochran-Mantel-Haenszel (CMH) Weights

Suppose that participants are randomly assigned into the active group or placebo group, stratified by K factors ( $K \geq 2$ ):

Strata	Response	Active Group	Placebo	Total
1	Yes	$x_{11}$	$x_{01}$	$x_1$
	No	$n_{11}-x_{11}$	$n_{01}-x_{01}$	$n_1-x_1$
	Total	$n_{11}$	$n_{01}$	$n_1$
2	Yes	$x_{12}$	$x_{02}$	$x_2$
	No	$n_{12}-x_{12}$	$n_{02}-x_{02}$	$n_2-x_2$
	Total	$n_{12}$	$n_{02}$	$n_2$
...				
K	Yes	$x_{1K}$	$x_{0K}$	$x_K$
	No	$n_{1K}-x_{1K}$	$n_{0K}-x_{0K}$	$n_K-x_K$
	Total	$n_{1K}$	$n_{0K}$	$n_K$

Morphic Therapeutic, Inc.  
Study Number: MORF-057-202

Statistical Analysis Plan  
Version 1.0, 16SEP2024

$n_{1j}$  is the number of participants randomized to the active group and  $x_{1j}$  is number of responders in the active group for strata j, and  $n_{0j}$  is the number of participants randomized to placebo and  $x_{0j}$  is number of responders in the placebo group for strata j.

The response rate difference  $\delta_j = p_{1j} - p_{0j}$  between active group and placebo for strata j is estimated by

$$\widehat{\delta}_j = \widehat{p}_{1j} - \widehat{p}_{0j}$$

Where the estimated response rate  $\widehat{p}_{1j} = x_{1j} / n_{1j}$  and  $\widehat{p}_{0j} = x_{0j} / n_{0j}$ .

The overall response rate difference is estimated by the stratified response rate difference using the CMH weights, which is calculated as

$$\widehat{\delta}_w = \sum_{j=1}^K w_j \widehat{\delta}_j$$

where  $w_j = (n_{1j}^{-1} + n_{0j}^{-1})^{-1} / [\sum_{j=1}^K (n_{1j}^{-1} + n_{0j}^{-1})^{-1}]$  is the weight for stratum j with  $\sum_{j=1}^K w_j = 1$ .

The 100  $(1 - \alpha)\%$  confidence interval of the overall response rate difference is given by

$$\widehat{\delta}_w \pm Z_{\alpha/2} \sqrt{\sum_{j=1}^k w_j^2 \widehat{V}(\widehat{\delta}_j)}$$

Where  $\widehat{V}(\widehat{\delta}_j) = (\widehat{p}_{1j}(1 - \widehat{p}_{1j})/n_{1j}) + (\widehat{p}_{0j}(1 - \widehat{p}_{0j})/n_{0j})$  is the estimated variance of the response rate difference in strata j and  $Z_{\alpha/2}$  is the  $(1 - \alpha/2)$  percentile of the standard normal distribution.

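### The default normal-approximation interval for single proportions under-covers when rates are low, and the subgroup risk-difference interval has no rule for sparse or empty strata

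*SAP*

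**What the plan says.** SAP Section 4 gives a general rule for proportions: "The confidence interval (CI) for the proportion will be calculated using the normal approximation approach when reported, unless otherwise specified". The SAP names no other method for a single proportion, so the default applies wherever such an interval is requested:

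- Section 4.8.3.1, Week 12: per-arm 95% intervals for the Table 6 endpoints by prior advanced therapy, baseline MES and baseline mMCS, and by-visit intervals for symptomatic and Partial MCS response.
- Section 4.8.3.1, Weeks 52 and 104: per-arm 95% intervals, overall and in the same three subgroup splits.
- Section 4.8.3.4: clinical remission, clinical response and corticosteroid-free remission at Week 104, and symptomatic remission.

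For the subgroup forest plots of the primary and secondary endpoints, Section 4.8.4 covers eight baseline factors and says "The computation will be based on the stratified risk difference using the Cochran-Mantel-Haenszel (CMH) weights", following the approach used in the overall population. Section 6.5 gives that formula. Its stratum term, which "is the estimated variance of the response rate difference in strata j", is the sum of unpooled p(1-p)/n terms, so the interval is of Wald type. Neither section says what to do when a stratum has few participants or none in one arm.

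**The concern.** The normal-approximation interval, read in its ordinary Wald form, takes its width from the observed proportion. When few events occur, that width is underestimated and the interval is centred too low. With no events it has zero width, which states certainty where there is very little information. Several Table 6 endpoints are strict (for example MES of 0, or MES of 0 together with histologic remission), and the plan reports them per arm within subgroups of a 70-participant arm. These are the conditions in which the method is weakest.

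The subgroup forest plots carry estimates and intervals but no p-values, so the interval is the only inference a reader sees. Within a subgroup that is not itself a stratification factor, the Section 6.5 formula splits the data into up to four strata.

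At stake is the honesty of the error bars in descriptive and subgroup displays, and the risk that empty-stratum handling is improvised after unblinding.

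**Working it through.** **Inputs from the SAP.** 70 per arm, allocated 1:1:1:1 (Sections 1.2, 1.3); two-sided alpha 0.10; assumed placebo remission 7%, hence 22% on active with the 15-point difference; 30-40% advanced-therapy experienced, so 0.30 × 70 = 21 to 0.40 × 70 = 28 per arm.

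**Assumptions, not in the SAP.** Low endpoint rates of 2-10%; subgroups of 14 and 7 per arm; a stratum mix of 35% experienced and 60% MES 3.

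**Step 1: the plan's own figure.** Section 1.3 says "A sample size of 70 participants per group (giving a total of 280) will provide 80% power to detect a difference of 15" points, "based on the use of a two-sided test at the alpha=0.10 level of significance". With the pooled-variance chi-squared formula, 7% vs 22% and n = 70, power is 81.5%. The stated 80% reproduces.

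**Step 2: single proportions.** Wald is p̂ ± 1.96·√[p̂(1−p̂)/n]. Exact coverage at true rate p is the sum of the binomial probabilities of every x whose interval contains p.

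| n | Wald, mean over 2-10% | Wilson, mean over 2-10% | Wald at 7% | Wilson at 7% | Wald at 22% |
|---|---|---|---|---|---|
| 70 | 89.2% | 95.6% | 86.7% | 97.0% | 94.9% |
| 28 | 77.7% | 95.9% | 86.6% | 95.7% | 95.2% |
| 21 | 68.9% | 95.5% | 78.0% | 94.5% | 95.4% |

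- *Zero width.* At 7%, the chance of no events is 0.93^28 = 13.1% at n = 28 and 0.93^21 = 21.8% at n = 21. For 0/21, Wald gives [0%, 0%] and Wilson 0-15.5%. For 0/28, Wilson gives 0-12.1%.
- *Negative lower limit.* This occurs when x > 0 and p̂ < 1.96²/(n + 1.96²), which is 1 to 3 events at each of these sizes. At 7% the chance is 26% (n = 70), 74% (n = 28) and 73% (n = 21).
- *Direction.* At n = 70 and 7%, the whole interval lies below the true rate in 12.4% of samples, against a nominal 2.5%. For 5/70, Wald is 1.1-13.2% (width 12.1 points) and Wilson is 3.1-15.7% (12.6 points). The fault there is mainly placement, not width.

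**Step 3: stratified risk difference.** Section 6.5: δ̂ = Σ w_j(p̂_1j − p̂_0j), with w_j proportional to (1/n_1j + 1/n_0j)⁻¹ and variance Σ w_j²[p̂_1j(1−p̂_1j)/n_1j + p̂_0j(1−p̂_0j)/n_0j]. Simulated at 22% vs 7%, the same rates in every stratum, with one-arm-empty strata given zero weight:

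| Per arm | Strata | Coverage of nominal 95% | At least one stratum empty in an arm |
|---|---|---|---|
| 70 | 4 | 94.0% | <0.1% |
| 28 | 2 | 93.2% | 0% |
| 21 | 2 | 92.0% | 0% |
| 28 | 4 | 91.5% | 3% |
| 21 | 4 | 89.7% | 10% |
| 14 | 4 | 85.2% | 31% |
| 7 | 4 | 61.2% | 84% |

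The experienced subgroup uses two strata, because Section 4.8.4 drops the duplicated factor. The small-subgroup figures depend on the stratum mix: a calculation with fixed stratum sizes gives 88.8% at 14 and 68.1% at 7 per arm.

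If n_1j or n_0j is 0, then p̂ is 0/0 and 1/n is undefined, so the formula as written returns no result.

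**Step 4: an illustration.** Unstratified, 4/28 vs 0/28: Wald gives 1.3 to 27.2 points and excludes zero; Newcombe gives −0.5 to 31.5 and does not.

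**The case against.** Much of the case on the other side stands, and it sets the limits of the point.

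- *The 7% rate.* Section 1.3 says "The calculation is based upon an assumed placebo remission rate of 7"%, for Week 12 clinical remission. A reader might infer that the 86.7% coverage describes a planned interval. It does not: Section 4.8.1.1 asks for intervals on the risk difference only, and Table 6 lists clinical remission at Week 52 only. There is no placebo treatment after Week 12. The 7% is therefore an analogue for other low-rate endpoints, for which the SAP gives no rates.
- *One point on a sawtooth.* At n = 70, Wald coverage is 94.2% at 6.5%, 91.7% at 8% and 94.8% at 9%. A single value can mislead, which is why averages over 2-10% are used. The average shortfall remains.
- *Far too narrow everywhere.* A reader might infer this. At 5/70 the widths differ by half a point, and near 22% coverage is about 95%.
- *Collapse of the risk-difference interval.* Its width is zero only if every contributing stratum has 0% or 100% response in both arms. At 21-28 per arm and 22% vs 7% that happens in about 0.1% of data sets or fewer.
- *Empty strata.* The weight tends to zero as an arm empties, so dropping the stratum is natural. That is a sensible convention, but it is not written down.
- *No decision depends on these intervals.* This is correct. Significance rests on CMH p-values (Sections 4.8.1.1, 4.8.2, 4.8.6), so an inference that the primary result is undermined is not supported.

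**Conclusion.** The point holds for single proportions with low rates. Section 4 fixes a default that covers on average about 89% at 70 per arm and 69-78% at 21-28 per arm over assumed rates of 2-10%, where Wilson gives about 95.5-96%. It also prints [0%, 0%] at zero events and often a negative lower limit. For endpoints with rates near 22% it is adequate.

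For subgroup risk differences the point is narrower. In the one subgroup whose size the SAP determines, coverage is about 92-93%; with four strata at the same 21-28 per arm it is about 90-92%. Serious failure (about 85% at 14 per arm, 61% at 7) depends on assumed subgroup sizes and stratum mix, since the SAP gives none for factors such as age 65 or over or immunomodulator use. The missing rule for a stratum empty in one arm is a gap whatever the sizes.

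The primary and secondary tests and the overall risk difference (about 94% coverage) are not materially affected.

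**What to change.** - **Section 4:** replace the normal-approximation default with Wilson (or Clopper-Pearson) intervals for single proportions.
- **Section 4.8.4:** name one score-type interval, Miettinen-Nurminen or Newcombe, for all subgroup risk differences. Do not switch between stratified and unstratified methods according to the data, because that would mix estimates within one forest plot.
- **Sections 4.8.4 and 6.5:** state in advance how a stratum with nobody in one arm is handled, for example with zero weight.
- **Section 4.8.1.1:** the overall CMH-weighted interval may stay.

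No test, endpoint or sample size changes. The cost is minor programming with standard SAS options, and some intervals become wider or asymmetric. The text should be settled before the database lock for the Induction Period analysis.
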